### 5.2.3 ABOUT – Product Experience Questionnaire

Product experience will be assessed via a subject self-reported outcome measure, part of the ABOUT toolbox [13]. The questionnaire consists of 3 multi-item scales and 2 single-item scales, arising from an adaptation and rewording of the modified cigarette evaluation questionnaire (mCEQ) [14] to Reduced Risk Products (RRPs) and the Product Evaluation Scale [15]. The questionnaire assesses the degree to which subjects experience the reinforcing effects of P4M3 Gen 2.0 with CA35 and CM 35 Cartridges use in CIG smokers switching to P4M3 compared to subjects continuing CIG smoking by measuring:

- Product satisfaction (satisfying, tastes good, enjoy the product), average of the item scores to questions 1, 2, and 12.
- Psychological rewards (calms down, more awake, less irritable, helps concentrate, reduces hunger), average of the item scores to questions 4, 5, 6, 7, and 8.
- Aversion (dizziness, nausea), average of the item scores to questions 9 and 10.
- Enjoyment of respiratory tract sensations (single-item assessment), item 3.
- Craving reduction (single-item assessment), item 11.

Subjects will be asked to assess the items of the questionnaire on a 7-point scale, ranging from 1= “not at all” to 7= “extremely”.

Symptoms or worsening of symptoms documented in the questionnaire do not need to be documented as additional AEs as the main source for AE collection will be the face-to-face interview between the subject and study site staff, using open, non-directive questions.

## 5.3 Categorical Variables

P4M3 Gen 2.0 is an ENDS utilizing tobacco sticks with two flavour variants in the corresponding randomization arms, CA35 (“Classic Auburn”) and CM35 (“Classic Menthol”), that will be compared to CIG (conventional cigarette; primary comparison), and SA (smoking abstinence; exploratory comparison) groups.

**Table 7 Categorical Variable Definitions**

Variable	Categories	Details
----------	------------	---------

#### Confidentiality Statement

Data and information contained in this document are considered to constitute trade secrets and confidential commercial information, and the legal protections provided to such trade secrets and confidential information are hereby claimed under the provisions of applicable law. No part of this document may be publicly disclosed without the written consent of Philip Morris Products S.A

Sex	Female Male	Stratification factor used for randomization and statistical analysis
Race	American Indian OR Alaska Native Asian Black Native Hawaiian OR Other Pacific Islander White	Stratification factor used for statistical analysis
BMI (kg/m  )	Normal $\geq 18.5$ and $< 25.0$ Overweight $\geq 25.0$ and $< 30.0$ Obese $\geq 30.0$ and $< 32.0$	Derived
	Note that patients with BMI $< 18.5$ (underweight) and $\geq 32$ (Obese) are excluded from the study as per the inclusion/exclusion criteria.	
FTND total score	Mild: 0-3 Moderate: 4-6 Severe: 7-10	Derived

## 5.4 Human Puffing Topography

Prior to calculation of the per-day parameters, the topography data will be processed by PMI through analysis software. Only valid data will contribute to the per-puff parameters (listed in [Table 4](#)) and will be part of the study database.

Per subject, the per-puff parameters (listed in [4](#)) part of the study database will be used to derive the per-day parameters listed in [Table 5](#) (using the formulas contained in that table).

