7.5.2 Human Puffing Topography Assessment

Human puffing topography (HPT) involves the measurement of each subject's unique way of using P4M3.

The miniaturized detachable external data recorder (MDED R) puffing topography device measures and records the flow rate, other per-puff parameters, and power setting of P4M3 as listed in [Appendix C](#). From the per-puff measurements, per-day parameters will be derived.

The MDED R puffing topography device will be used with the P4M3 on Day 1 to Day 5 with data recording during *ad libitum* use. Data will not be collected during CIG smoking.

The P4M3 is equipped with a pressure sensor, which measures the pressure at the Cartridge level. When a puff is drawn, the P4M3 calculates the difference of pressure between the atmospheric pressure and the pressure measured at the Cartridge level. The aerosol production (heating cycle) is then triggered based on the difference of pressure values calculated by the P4M3. The MDED R puffing topography device allows to collect these data when it is mechanically attached to the Battery Unit of P4M3 and electronically connected to its USB port. The MDED R puffing topography device works as a data logger. Once connected to the P4M3, the MDED R puffing topography device will record HPT data. Any malfunction of the MDED R puffing topography device will be documented in the appropriate log.

One MDED R puffing topography device will be assigned at Day -1 for each subject and will be used for all further HPT assessments. A replacement device will be provided in case of malfunction of the device assigned. The Sponsor will provide training on the use of the MDED R puffing topography device to the investigational site staff which will be responsible for the HPT assessment. All MDED R puffing topography devices will be returned to the Sponsor after completion of the study.

Prior to calculation of the parameters, the Sponsor's HPT group will process, validate, and discard any invalid data, as per the Sponsor's SOPs. The Sponsor will provide copies of both the raw and validated HPT datasets to the Investigator. Only valid data will be part of the study database and will be analyzed.

Confidentiality Statement

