**Table 5 Per-Day Parameters**

Parameter	Variable	Formula	Unit
Total number of puffs/day	NPC	Count Ni	
Total puff volume	TVOL	$\sum Vi$	mL
Total puff duration/day	TDi	$\sum Di$	s
Average puff volume	AvgVi	$\sum Vi / NPC, i=1 \dots NPC$	mL
Average puff duration	AvgDi	$\sum Di / NPC, i=1 \dots NPC$	s
Average flow	AvgQmi	$\sum Qmi / NPC, i=1 \dots NPC$	mL/s

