#### 9.6.4.5 Exploratory Objective 5: Human Puffing Topography

Separately for each Day = 1, 2, 3, 4, and 5, the per-day parameters (Table 5) will be considered as continuous variables and summarised as described in section 9.1.3 on the P4M3 arm (CA35 or CM35 combined and separately), except that no change from baseline can be computed.

For each subject, the per-day parameters (Table 5) will be averaged over days 1-5. These averages per subject will then be considered as continuous variables and summarised as described in section 9.1.3 on the P4M3 arm (CA35 or CM35 combined and separately), except that no change from baseline can be computed.

---

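### Puffing-topography day totals carry no condition that the day was fully recorded, so a partly recorded day enters as a complete one and biases those totals downward

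*SAP*

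**What the plan says.** Protocol 7.5.2 has the sponsor's HPT group handle the recorder files before any parameter is calculated: under its SOPs it "will process, validate, and discard any invalid data". Only what survives enters the study database. On recorder failure the same section says: "Any malfunction of the MDED R puffing topography device will be documented in the appropriate log". It also provides a replacement device.

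SAP 5.4 repeats the filter ("Only valid data will contribute to the per-puff parameters") and says that the per-puff records that are "part of the study database will be used to derive the per-day parameters". SAP Table 5 gives the formulas:

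- NPC, labelled "Total number of puffs/day", is Count Ni.
- TVOL is the sum of Vi.
- TDi is the sum of Di.

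SAP 9.6.4.5 summarises these for each of Days 1 to 5, and then, for each subject, "the per-day parameters (Table 5) will be averaged over days 1-5". Neither document states a minimum recording time, a minimum number of days, or a link from the malfunction log to the derivation.

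**The concern.** A filter that keeps only valid puffs suits a mean per puff. A total also needs the recording to cover the whole day. If the recorder stops at midday, puffs taken in the afternoon leave no trace, and Count Ni returns the morning's puffs as the day's figure.

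The plan foresees such failures. Protocol 7.5.2 logs them, and Protocol 8.7 collects product events affecting the MDEDR, with a category for intermittent power loss. Replacing the device shortens an outage but does not recover the puffs.

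The planned outputs would not show the problem. SAP 9.1.3 reports how many subjects have missing data, but a half-recorded day gives a number, not a missing value. The SAP does set completeness rules elsewhere: SAP 9.1.5.2 has a 50% item threshold for the ABOUT questionnaire and sets the FTND score to missing if any item is missing. HPT has no counterpart.

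At stake is the accuracy of three descriptive totals under exploratory objective 5, which sets out to describe topography over the entire exposure period.

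**Working it through.** The documents give no HPT loss rate, so there is no figure of the plan's to reproduce. What follows shows how the stated formulas behave under assumed losses.

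**1. Effect on one day.** If a fraction f of the day's real puffs is unrecorded at random, NPC, TVOL and TDi are each multiplied by (1 − f). I applied the Table 5 formulas to an assumed day of 200 puffs, with 2,000 random removals at each f:

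| f | NPC, TVOL, TDi (ratio to truth) | AvgVi, AvgDi (ratio to truth) |
|---|---|---|
| 5% | 0.95 | 1.00 |
| 10% | 0.90 | 1.00 |
| 20% | 0.80 | 1.00 |
| 50% | 0.50 | 1.00 |

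Mean puff volume and duration hold up; the totals fall in proportion. Mean inter-puff interval and puff frequency depend on a choice that the SAP does not state. At f = 20% they stay at 1.00 if the recorded intervals are kept, and move to about 1.25 and 0.81 if intervals are recomputed between surviving puffs.

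**2. Effect on a subject's 5-day mean.** With d affected days, each losing a fraction f, and similar use across days:

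ratio = (5 − d + d(1 − f)) / 5

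- d = 1, f = 0.25: (4 + 0.75)/5 = 0.95
- d = 1, f = 0.50: (4 + 0.50)/5 = 0.90
- d = 2, f = 0.50: (3 + 1.00)/5 = 0.80

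**3. Effect on an arm.** With the planned 18 subjects per P4M3 arm and similar use between subjects, one subject with one half-lost day lowers the arm's 5-day mean by 10%/18 ≈ 0.6%, and that day's arm mean by 50%/18 ≈ 2.8%. If every subject lost half of one day, the 5-day arm mean would fall by the full 10%.

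**4. With incomplete days set to missing.** The subject's mean is taken over the 5 − d complete days: (5 − d)/(5 − d) = 1.00, provided use is similar across days.

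**The case against.** The strongest reply is that validation follows sponsor SOPs outside these documents, and a completeness check may sit there. Recorders are individually assigned, staff are trained, and failed devices are replaced, all in confinement, so outages may be few and short. This stands as a limit on size. It does not supply a rule: as written, the protocol and SAP would average a partly recorded day as a full one.

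A reader might infer more than the documents support:

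- **That P4M3 use is understated.** It is not. Product use is exploratory objective 3, analysed under SAP 9.5 from cartridge counts and e-liquid weight, neither of which depends on the recorder.
- **That a day with no records counts as zero, costing 20% (1/5) of the 5-day mean.** Nothing says so. Such a day has no per-puff records to derive from, and Protocol 12.1.4 leaves missing values unimputed (SAP 9.1.5.1 repeats this under laboratory parameters). Missing is the natural reading, with no downward shift.
- **That every discarded record is a real puff.** The validity criteria are not given. Artefacts may be among the discards, and removing those is correct.
- **That totals should be rebuilt from the raw file, or scaled up by the mean valid puff.** The former departs from Protocol 7.5.2, under which only valid data are analysed; the latter is an imputation that assumes lost puffs resemble retained ones.

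**Conclusion.** The point holds for NPC, TVOL and TDi on partly recorded days. The stated derivation gives a total that is too low whenever real puffs went unrecorded, and the planned missing-data counts cannot reveal it. Half of one day in five costs 10% of that subject's 5-day mean; two such days cost 20%. These figures assume similar use across days and are illustrative, because the actual loss is unknown and could be negligible.

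HPT is exploratory and descriptive, with no test attached, and it does not enter the primary, key secondary or safety analyses. This is a cheap improvement of minor severity.

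**What to change.** In SAP 5.4 and 9.6.4.5:

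1. Set NPC, TVOL and TDi to missing for any subject-day on which the MDEDR log shows a malfunction or there was unrecorded P4M3 use. State how unrecorded use is identified; dispensing and return times (Protocol 6.5.1) and cartridge weights (Protocol 7.5.3) are already collected.
2. Average the three totals over fully recorded days only.
3. Report, by arm, the number of fully recorded days and the number of discarded puff records.

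The cost is a few lines of SAP text and programming, plus discard counts, which can be obtained by comparing the raw and validated datasets that the sponsor already holds. The downside is slightly fewer subject-days in the totals, and a 5-day mean that may rest on fewer than five days, which item 3 makes visible.

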## 5.5 CYP1A2

CYP1A2 activity will be assessed in plasma by measuring paraxanthine (PX) and caffeine (CAF) concentrations and calculating the PX/CAF molar metabolic ratio, both expressed in molar equivalent (nmol/L), and calculated as follows:

### Confidentiality Statement

Data and information contained in this document are considered to constitute trade secrets and confidential commercial information, and the legal protections provided to such trade secrets and confidential information are hereby claimed under the provisions of applicable law. No part of this document may be publicly disclosed without the written consent of Philip Morris Products S.A

$$\frac{PX}{CAF} = ((PX_c [\text{ng/mL}]/180.17 [\text{ng/nmol}]) * [1000\text{mL/L}]) / ((CAF_c [\text{ng/mL}]/194.19 [\text{ng/nmol}]) * [1000\text{mL/L}])$$

PX The molecular weight is 180.16 g/mol (National Center for Biotechnology Information (NCBI). PubChem CAS:611-59-6 [16]).

CAF The molecular weight is 194.19 g/mol. (National Center for Biotechnology Information (NCBI). PubChem CAS:58-08-2 [17]).

The converted results will be reported as a percentage.

## 6 SAMPLE SIZE JUSTIFICATION

In this study, 72 subjects are randomized as follows:

- 36 in combined P4M3 arms (18 in CA35 and 18 in CM35),
- 18 in CIG arm,
- 18 in SA arm.

Based on four previous similar studies conducted by PMI on the tobacco heating system (another alternative product to CIG developed by PMI which is likely to be less risky than cigarette; ClinicalTrials.gov identifiers are NCT01970995, NCT01989156, NCT01959932, and NCT01970982, respectively), Table 8 contains estimates of geometric mean ratios (GMR) and associated coefficients of variations (GCV) for the (adjusted) contrast of a tobacco heating system against CIG. The effect of P4M3 is expected to be similar (or better) on the BoExp selected in this study compared to this tobacco heating system. In addition, based on these studies, up to 15% of missing values may be expected for various reasons (e.g., withdrawals, mis-randomization, etc.).

Using the statistics displayed in Table 8, the sample size planned for this study accounting for 15% of missing values (resulting in 30 and 15 subjects in P4M3 combined and CIG arms, respectively), and a one-sided two-sample t-test (on the log-scale) with 2.5% type I error probability, the estimated power for each BoExp is displayed in Table 8. By multiplying the power for each individual BoExp over the four to be tested in the primary hypothesis (per study), a global estimate of power is also obtained.

Note that 10,000 simulations of one-sided two-sample t-test were also conducted to determine the 90 percentiles of the (upper) half-width of the 97.5%-confidence interval (CI) of the ratio between P4M3 and CIG, as well as the 90 percentiles of the upper bounds of these CIs. These are also displayed in Table 8. These provide indications on the expected precision on the estimates of the ratios.

**Table 8 Power Computations for Primary Objective**

NCT (Region)	Endpoint	GMR (%)	GCV (%)	Power	Overall Power	90%iles of the upper half-width of CI(%)	90%iles of the upper bound of CI (%)
1970995 (JP)	2CyEMA	18.23	32.43	>99%	>99%	4.9	25.4
	3-HPMA	50.67	32.72	>99%		13.8	71
	COHb	44.94	17.24	>99%		6	53.8
	Total NNAL	43.69	26.09	>99%		9.2	57.1
1989156 (US)	2CyEMA	17.23	42.01	>99%	>99%	6.2	26.3
	3-HPMA	45.77	36.45	>99%		14.1	66.3
	COHb	38.14	26.5	>99%		8.2	50.3
	Total NNAL	43.81	40.7	>99%		15.3	65.9
1959932 (EU)	2CyEMA	13.16	34.41	>99%	>99%	3.8	18.7
	3-HPMA	41.63	26.1	>99%		8.7	54.4
	COHb	23.45	16.84	>99%		3.1	28
	Total NNAL	43.54	27.13	>99%		9.6	57.5
1970982 (JP)	2CyEMA	21.21	43.16	>99%	>99%	7.9	32.7
	3-HPMA	52.86	39.57	>99%		17.8	78.9
	COHb	47.1	16.08	>99%		5.8	55.6
	Total NNAL	49.03	42.51	>99%		18	75.3

Table 8 shows that the power of this study for the primary objective is expected to be at least 99%.

A similar reasoning and assumptions for the 1st key secondary objective can be made. Table 9 displays the power estimates for the 1st key secondary hypothesis with a power of at least 99%.

**Table 9 Power Computation for 1st Key Secondary Objective**

NCT (Region)	Endpoint	GMR (%)	GCV (%)	Power	Overall Power	90%iles of the upper half-width of CI (%)	90%iles of the upper bound of CI (%)
1970995 (JP)	3-HMPMA	43.06	35.59	>99%	>98%	12.9	62
	3-OH-B[a]	27.19	43.93	>99%		10.4	42
	S-PMA	10.97	46.63	>99%		4.5	17.4
	Total NNN	27.02	61.84	>99%		15.5	49.1
1989156 (US)	3-HMPMA	38.26	53.56	>99%	>98%	18.4	64.6
	3-OH-B[a]	28.94	54.77	>99%		14.3	49.4

#### Confidentiality Statement

Data and information contained in this document are considered to constitute trade secrets and confidential commercial information, and the legal protections provided to such trade secrets and confidential information are hereby claimed under the provisions of applicable law. No part of this document may be publicly disclosed without the written consent of Philip Morris Products S.A

	S-PMA	12.58	69.68	>99%		8.4	24.4
	Total NNN	14.06	78.93	>99%		10.8	29.1
1959932	3-HMPMA	22.54	30.76	>99%	>98%	5.7	30.9
(EU)	3-OH-B[a]	27.5	46.17	>99%		11.1	43.5
	S-PMA	5.99	37.3	>99%		1.9	8.8
	Total NNN	24.12	95.15	>99%		22.9	55.7
1970982	3-HMPMA	37.71	49.07	>99%	>98%	16.4	61.6
(JP)	3-OH-B[a]	29.99	52.2	>99%		14	50.2
	S-PMA	15.68	49.76	>99%		6.9	25.6
	Total NNN	30.06	67.69	>99%		19.2	57.4

For the key secondary objectives 2 to 5, a similar reasoning is applied, but this time, a sample of size of 15 for the P4M3 (CA35 or CM35) arms needs to be used and 15 subjects in the CIG arm (with 15 subjects) (Table 10 and Table 11). As per Table 10 and Table 11, the power was at least of 99% for each BoExp in the previous studies.

By multiplying the power for each objective ( $\approx 99\%$ ) across all 6 objectives (1 primary + 5 key secondary), the power for all objectives altogether is then estimated to be at least 94% ( $= 0.94 \approx 0.99^6$ , assuming independence of the 6 objectives, each with a 99% power).

**Table 10 Power Computations for Key Secondary Objectives 2 & 4**

NCT (Region)	Endpoint	GMR (%)	GCV (%)	Power	Overall Power	90%iles of the upper half-width of CI (%)	90%iles of the upper bound of CI (%)
1970995	2CyEMA	18.23	32.43	>99%	>95%	6.1	26.9
(JP)	3-HPMA	50.67	32.72	>99%		17.2	75.2
	COHb	44.94	17.24	>99%		7.3	55.4
	Total NNAL	43.69	26.09	>99%		11.3	59.7
1989156	2CyEMA	17.23	42.01	>99%	>95%	7.8	28.3
(US)	3-HPMA	45.77	36.45	>99%		17.5	70.7
	COHb	38.14	26.5	>99%		10.1	52.7
	Total NNAL	43.81	40.7	>99%		19.3	71
1959932	2CyEMA	13.16	34.41	>99%	>95%	4.7	19.8
(EU)	3-HPMA	41.63	26.1	>99%		10.8	56.9
	COHb	23.45	16.84	>99%		3.7	28.8
	Total NNAL	43.54	27.13	>99%		11.9	60.4
1970982	2CyEMA	21.21	43.16	>99%	>95%	9.9	35
(JP)	3-HPMA	52.86	39.57	>99%		22.4	84.4

#### Confidentiality Statement

Data and information contained in this document are considered to constitute trade secrets and confidential commercial information, and the legal protections provided to such trade secrets and confidential information are hereby claimed under the provisions of applicable law. No part of this document may be publicly disclosed without the written consent of Philip Morris Products S.A.

COHb	47.1	16.08	>99%	7.1	57.2
Total NNAL	49.03	42.51	>99%	22.5	80.9

**Table 11 Power Computations for Key Secondary Objectives 3 & 5**

NCT (Region)	Endpoint	GMR (%)	GCV (%)	Power	Overall Power	90%iles of the upper half-width of CI (%)	90%iles of the upper bound of CI (%)
1970995 (JP)	3-HMPMA	43.06	35.59	>99%	>94%	16.0	65.9
	3-OH-B[a]	27.19	43.93	>99%		13.0	45.2
	S-PMA	10.97	46.63	>99%		5.6	18.9
	Total NNN	27.02	61.84	>99%		19.8	54.2
1989156 (US)	3-HMPMA	38.26	53.56	>99%	>94%	23.2	70.4
	3-OH-B[a]	28.94	54.77	>99%		18.2	54.2
	S-PMA	12.58	69.68	>99%		10.7	27.3
	Total NNN	14.06	78.93	>99%		14.0	33.1
1959932 (EU)	3-HMPMA	22.54	30.76	>99%	>94%	7.1	32.6
	3-OH-B[a]	27.5	46.17	>99%		14.0	47.2
	S-PMA	5.99	37.3	>99%		2.4	9.3
	Total NNN	24.12	95.15	>99%		30.0	64.6
1970982 (JP)	3-HMPMA	37.71	49.07	>99%	>94%	20.6	66.5
	3-OH-B[a]	29.99	52.2	>99%		17.8	55.1
	S-PMA	45.68	49.76	>99%		8.8	27.9
	Total NNN	30.06	57.69	>99%		24.6	63.8

## 7 CHANGES FROM THE PROTOCOL SPECIFIED STATISTICAL ANALYSES

- Addition of the definition of the Screened Population,
- Clarification of the Per Protocol Set (PPS),
- Clarification of the Safety Set (SAF),
- Clarification on safety follow-up periods:
  - Exposure period ends either on Day 5, 11:00 PM or early discontinuation date and time,
  - Follow-up period starts with end of exposure.

## 8 ANALYSIS SETS

### 8.1 Screened Population

The Screened Population consists of all subjects who signed the ICF and who underwent at least one of the screening procedures.

### 8.2 Full Analysis Set (FAS)

The Full Analysis Set (FAS) consists of all randomized subjects who have at least one post-randomization product use experience (if randomized to CIG or one of the P4M3 arms) and who have at least one valid non-safety assessment. The FAS will be analyzed by randomized study arm.

### 8.3 Per Protocol Set (PPS)

The Per Protocol Set (PPS) is a subset of FAS and includes all randomized subjects who fulfil key compliance criteria of the protocol, i.e., have no major protocol deviation impacting the evaluability of the primary objective. The PPS will be analyzed by randomized study arm.

### 8.4 Safety Set (SAF)

The Safety Set (SAF) population will consist of all the subjects with at least one exposure to P4M3 (product test at Admission Day -2), and who have at least 1 valid value for a safety assessment. The SAF will be analyzed according to randomized study arm or a group of enrolled but not randomized subjects when applicable (there is an exception to this rule and mis-randomized subjects will be assigned to their actual exposure arm, see [Table 12](#)).

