12.1.2 Definitions for Statistical Data Analysis

The following definition will be used for the statistical analysis of safety data:

Term	Definition
Actual exposure arm	
Categorical variable representing the actual study arm of enrolled subjects. Non-randomized subjects will be assigned to the category 'Enrolled but not randomized'. Randomized subjects will be assigned to the category corresponding to their randomization study arm.
 
In case of mis-randomization (use of a different product from the allocated one, use of a TNP while being assigned to the smoking cessation arm, or be smoking abstinent while being assigned to the CIG or one of the P4M3 arms), subjects will be assigned to the arm corresponding to their actual exposure.

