12.3.3 Safety Set (SAF)

The safety population will consist of all the subjects enrolled in the study with at least one exposure to P4M3 (product test at Admission Day -2), and who have at least 1 valid value for a safety assessment. The SAF will be analyzed according to actual exposure arm (see definition in section 12.1.2).

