#### **Table 12 Major Protocol Deviations with Impact on Evaluability**

##### **Confidentiality Statement**

---

Data and information contained in this document are considered to constitute trade secrets and confidential commercial information, and the legal protections provided to such trade secrets and confidential information are hereby claimed under the provisions of applicable law. No part of this document may be publicly disclosed without the written consent of Philip Morris Products S.A.

---

Category	Description
Any violation of inclusion/exclusion criteria	Considered a major deviation. The blinded data review team will decide on whether it impacts evaluability.
Mis-randomization (wrong information provided to randomization system)	Considered a major deviation with impact on evaluability.  Mis-randomized subjects will be classified according to their actual exposure arm for safety analysis.
Use of any nicotine or tobacco-containing product other than the assigned product during the exposure period	Considered a major deviation. The blinded data review team will decide on whether it impacts evaluability.
Assessments related to the primary objective performed outside the time tolerance (see Table 13 )	Considered a major deviation. The blinded data review team will decide on whether it impacts evaluability.

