#### 9.1.4 Definitions for Statistical Data Analysis

At the time of the present protocol, no new terms are defined.

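### The SAP defines mis-randomization more narrowly than the protocol, so a subject who used another product would stay in the randomized arm for safety

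*SAP*

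**What the plan says.** **Protocol.** Section 12.3.3 reads: "The SAF will be analyzed according to actual exposure arm", and refers to 12.1.2 for the meaning. Under 12.1.2 a randomized subject is counted in the randomized arm by default, and enrolled subjects who were never randomized form their own group. In mis-randomization, "subjects will be assigned to the arm corresponding to their actual exposure". The section spells out three situations: use of a product other than the one allocated, use of any tobacco or nicotine product in the abstinence arm, and abstinence in the CIG arm or a P4M3 arm. Sections 12.4 and 12.6.2 apply the actual exposure arm to Safety Set demographics and to safety listings and summaries.

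**SAP.** Section 8.4 sets the default: "The SAF will be analyzed according to randomized study arm or a group of enrolled but not randomized subjects when applicable". It adds in parentheses: "there is an exception to this rule and mis-randomized subjects will be assigned to their actual exposure arm", and points to Table 12. The relevant row of Table 12 is labelled "Mis-randomization (wrong information provided to randomization system" (the closing parenthesis follows), and it carries the safety instruction: "Mis-randomized subjects will be classified according to their actual exposure arm for safety analysis". A separate row covers "Use of any nicotine or tobacco-containing product other than the assigned product during the exposure period". That row leaves evaluability to the blinded review team and says nothing about safety classification. Abstinence in a product arm has no row. Sections 9.3 and 9.6.5.1 present Safety Set data by randomized arm and do not repeat the exception. Section 9.1.4 says: "At the time of the present protocol, no new terms are defined". Section 7 lists the Safety Set entry as a clarification and does not mention mis-randomization.

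**The concern.** Safety and tolerability are the study's secondary objective, and the tables will be read as a comparison of products. The protocol's safety definition is written so that a subject whose use did not match the allocation is counted under what was actually used. The SAP keeps the word for that exception but attaches it to a different event. The subjects the protocol intended to move are then no longer those the SAP moves, and an adverse event in such a subject would be reported under an arm whose product, or abstinence, did not describe that subject's exposure.

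The difference is also hard to see. The SAP uses the term actual exposure arm in 8.4 and Table 12 but defines it nowhere, and a programmer working from the SAP alone would follow Table 12. Protocol 12.1 asks that changes to the planned methods be documented in the SAP, and a one-line entry calling this a clarification does not show that the definition changed.

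**Working it through.** The plan states no figure on this point, so there is nothing to reproduce. The check compares the two rules and then gives a sense of scale.

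**The two rules side by side**

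| Situation | Protocol 12.1.2 and 12.3.3 | SAP 8.4 and Table 12, as written |
|---|---|---|
| Randomized, used the allocated product | Randomized arm | Randomized arm |
| Enrolled, not randomized | Separate group | Separate group |
| Used a different product | Actual exposure arm | Randomized arm |
| Tobacco or nicotine use in the SA arm | Actual exposure arm | Randomized arm |
| Abstinent in the CIG arm or a P4M3 arm | Actual exposure arm | Randomized arm (no row in Table 12) |
| Wrong information entered in the randomization system | Not named in the definition | Actual exposure arm |

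The first two rows agree. The next three are the conflict. In the last row, the only input to randomization that either document names is sex (Protocol 6.3, SAP 4.6.1). A subject whose sex was entered wrongly still receives an arm and would normally use that arm's product, so randomized and actual arm would usually be the same and the SAP exception would rarely move anyone.

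**Scale**

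Inputs:
- 72 subjects in four equal arms: 72/4 = 18 per arm (Protocol 4.1 and 12.9.4, SAP 4.1).
- Assumption: all 18 in each arm are in the Safety Set.
- Assumption: k subjects randomized to SA smoke cigarettes, each has one adverse event with the same preferred term, and nobody else has it. Neither document gives an expected k, so k = 1 to 3 is shown.

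Formulas:
- SAP rule: SA incidence = k/18; CIG incidence = 0/18.
- Protocol rule: SA incidence = 0/(18 − k); CIG incidence = k/(18 + k).

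Results:

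| k | SAP: SA | SAP: CIG | Protocol: SA | Protocol: CIG |
|---|---|---|---|---|
| 1 | 1/18 = 5.6% | 0/18 = 0% | 0/17 = 0% | 1/19 = 5.3% |
| 2 | 2/18 = 11.1% | 0/18 = 0% | 0/16 = 0% | 2/20 = 10.0% |
| 3 | 3/18 = 16.7% | 0/18 = 0% | 0/15 = 0% | 3/21 = 14.3% |

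For one subject, SA differs by 5.6 percentage points between the rules and CIG by 5.3. The amounts are not equal because the arm sizes change with the reassignment.

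**The case against.** Several points on the other side are sound.

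- **Same structure.** A reader might infer that the SAP abandoned an actual-exposure analysis for a randomized-arm one. The documents do not support that. Protocol 12.1.2 also counts randomized subjects in their randomized arm unless they are mis-randomized, and SAP 8.4 has the same three parts. The departure is the definition of the exception, not the default.
- **The protocol uses the term in two ways.** Protocol 11.1.2 lists mis-randomization and other-product use as separate deviations, and Table 12 follows that split. This explains where the SAP wording may come from. It does not remove the conflict, because 12.1.2 is the definition written for safety analysis and 12.3.3 cites it.
- **The protocol definition may carry over.** The SAP calls itself a supplement to the protocol analyses, and 9.1.4 defines no new terms. On that reading 12.1.2 still governs. But SAP 8.4 refers to Table 12, not to the protocol, and Table 12 gives its own meaning. At best, two definitions stand together.
- **The SAP exception might move someone.** A reader might infer that it is empty. That is likely but not shown: neither document lists every input to the randomization system, and a wrong entry could conceivably lead to a different product being dispensed.
- **The common-event list.** SAP 9.6.5.1 calls an event common at 5% or more in any arm, and a reader might infer that misplacing one subject changes that list. It does not in the example: 5.6% in SA and 5.3% in CIG both pass, so the term is common under either rule. With 18 per arm, any single event passes 5%, correctly placed or not.
- **Off-arm use should be rare and visible.** Use is confined, dispensed by the site and logged, deviations are listed, and no inference is made on safety. All this limits the consequence. It does not close the route: adverse events before discontinuation and in the follow-up still have to be assigned to an arm. The documents also disagree on what follows off-arm use. Protocol 5.2 and SAP 4.5.3 list non-adherence among reasons for mandatory discontinuation, while Protocol 4.1 and SAP 4.1 leave it to the investigator. Those passages must be reconciled.
- **The protocol wording is incomplete.** It sets no amount of off-arm use. Read literally, one cigarette in the SA arm would move the whole subject to CIG, and a P4M3 user who stops late could be moved to SA together with events that arose during P4M3 use. This stands, and the repair has to deal with it.

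**Conclusion.** The point holds as an unreconciled difference in definition. Followed as written, the SAP leaves in the randomized arm the subjects whom Protocol 12.1.2 and 12.3.3 would count by actual exposure, and SAP section 7 does not disclose this as a change.

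The size is conditional. No misattribution follows unless off-arm use occurs, and the documents give no expected number. If one SA subject smokes and has an event, the tables show SA 5.6% and CIG 0% under the SAP, against SA 0% and CIG 5.3% under the protocol, assuming 18 per arm in the Safety Set and no other such event. Safety is descriptive, so no hypothesis test, type I error or primary conclusion is affected. It is worth correcting because safety is the secondary objective, arms are small and the correction is cheap.

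**What to change.** - **SAP 9.1.4:** restate the Protocol 12.1.2 definition of actual exposure arm, with its three situations.
- **SAP 8.4, 9.3 and 9.6.5:** present Safety Set data by that variable. Randomized-arm safety tables can be kept as supplementary.
- **SAP Table 12:** rename the row on wrong input to the randomization system as randomization entry error. In the row for other-product use, state the safety classification, and cover abstinence in a product arm as well. The evaluability entries concern the Per Protocol Set and are outside this point.
- **Mixed or partial use:** add an analysis rule fixed before database lock. One option is to classify by the predominant product used in the exposure period and to list the adverse events of mixed-use subjects with the product in use at onset.
- **Protocol 11.1.2 and 12.1.2:** reconcile the two uses of mis-randomization, so that the deviation category and the safety definition have different names.
- **SAP section 7:** list whatever departs from the protocol. If the narrower rule is intended, record it there as a change with a reason.

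The cost is SAP wording and one derived variable. Product distribution and return are already logged (Protocol 6.5.4, SAP 4.6.3), so no new data are needed.
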